7.8.1.5 Adverse events of particular note

Gastro-intestinal adverse events (diarrhoea, nausea, vomiting, dehydration, weight decrease and decreased appetite) are considered as AEs of particular note.

Specific tables will be created in order to describe adverse events of particular note over 52 weeks:

- Summary of AEs including intensity, seriousness, clinical consequences (permanent dose reduction, drug discontinuation or drug interruption), drug relationship, therapy for event and outcome
- Summary of AEs including time to onset, number and duration of episodes

Depending on the number of patients having such AEs, a Kaplan-Meier plot of time to first adverse event of particular note may be drawn by treatment.

In addition, for pairs of selected adverse events (from diarrhoea, nausea, vomiting, decreased appetite, dehydration, weight decreased as defined in [Table 7.8.1.4: 1](#)), the frequency of patients with concurrent AEs will be summarised by treatment where concurrence is defined as an overlap of at least one day.

7.8.1.6 Adverse event analyses over the whole trial

Time at risk analyses of AEs will be presented for the overall timeframe. Time at risk and incidence rates per 100 patient years will be calculated based on the first onset of an AE.

An overall summary of adverse events will be presented.

A summary by treatment, primary system organ class (SOC) and preferred term (PT) will be presented. This will also be presented restricted to incidence in preferred term > 5% (in at least one treatment arm).

Separate tables will be provided for patients with other significant AEs according to ICH E3 ([11](#)), for patients with serious AEs (SAEs), for patients with severe AEs, for patients with AEs leading to permanent dose reduction, for patients with AEs leading to permanent dose discontinuation, for patients with investigator defined drug-related AEs, for patients with AEs leading to death, for investigator defined drug-related SAEs, for investigator defined drug-related AEs leading to death. The summary of patients with SAEs will also be presented restricted to incidence in preferred term > 1% (in at least one treatment arm).

Time at risk analyses of AEs pre-specified AESI will be summarised by treatment, primary SOC and preferred term.

Time at risk analyses of AEs, investigator defined drug-related AEs and SAEs within groupings by system will be summarised by treatment, safety topic and preferred term.

Adjudicated AEs will be analysed similarly as planned in [Section 7.8.1.3](#), except based on time at risk analyses.

7.8.2 Laboratory data

The analyses of laboratory data will be descriptive in nature and will be based on BI standards ([12](#)). This will be performed for the safety analysis over 52 weeks and overall.

Please refer to Section 7.3.4 of the CTP for further details.

In addition a thorough description of liver enzymes and bilirubin elevations over the whole study period will be given, according to the definitions in [Section 5.4.4](#), including a display of maximum individual elevation and a Kaplan-Meier plot of time to first liver enzyme elevation (if sufficient number of events).

A similar summary table of liver enzymes and bilirubin elevations over the first 52 weeks will also be provided (please refer to [Table 6.7: 3](#) for time windowing definition).

The time to onset of first liver enzyme and bilirubin elevation [days] will be summarised by categories (≤ 21 ; $>21-\leq 42$; $>42-\leq 63$; >63).

For each patient having experienced a liver enzyme and bilirubin elevation, a graphical representation of AST, ALT and bilirubin over time will be provided.

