4.2.1.2 Management of liver enzyme elevation

Evaluate the concomitant use of other drugs known to cause liver enzyme elevations. For a detailed guidance on how to manage liver enzyme elevations, please refer to Table 4.2.1.2: 1.

Table 4.2.1.2: 1: Recommendations for managing liver enzyme elevations

	AST or ALT increase to			Signs of hepatic injury*
	>1.5x to <3x ULN	≥3x to <5x ULN and no signs of hepatic injury (Section 5.3.6)	≥5x to <8x ULN and no signs of hepatic injury (Section 5.3.6)	(Section 5.3.6)
Visit 2 (randomization)	Withdraw trial medication or justify continuation ¹	Withdraw trial medication	Withdraw trial medication	Withdraw trial medication
Any other Visit	Continue as planned ²	Reduce dose or interrupt trial medication ³	Interrupt trial medication	Withdraw trial medication CLINICAL
		Close observation ⁴	Close observation ⁴	EVALUATION OF HEPATIC-INJURY (Section 5.3.6)
		After 2 weeks or any time later	After 2 weeks or any time later	
	<3x ULN	≥3x ULN	<3x ULN	>3x ULN
	Reduced: return to initial dose.	Permanently discontinue trial medication	Restart at reduced dose	Permanently discontinue trial medication.
	Interrupted: restart at reduced dose. Monitor bi- weekly for at least 8 weeks	Close observation ⁴	Monitor weekly for 4 weeks, then bi-weekly for at least 8 weeks	Close observation ⁴

Footnotes:

*Signs of hepatic injury are defined as

- ALT and/or AST ≥8 fold ULN
- ALT and/or AST ≥3 fold ULN and total bilirubin ≥2 fold ULN
- ALT and/or AST ≥3 fold ULN and unexplained INR >1,5
- ALT and/or AST ≥3 fold ULN and unexplained eosinophilia (>5%)
- ALT and/or AST ≥3 fold ULN and appearance of fatigue, nausea, vomiting, right upper abdominal quadrant pain or tenderness, fever and/or rash

phosphatase, total bilirubin, and eosinophils within 48 to 72 hours, then approximately 7 days, then approximately 2 weeks by using intermediate visit lab kit.

¹ Investigator to confirm in writing that continuation is justified (e.g. intermittent fluctuation of transaminases).

² According to visit schedule. Consider additional control visits as adequate.

³ To be decided by Investigator, based on individual risk assessment.

⁴Close observation: Re-test ALT and AST, alkaline

Page 43 of 126

Proprietary confidential information © 2018 Boehringer Ingelheim International GmbH or one or more of its affiliated companies

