5.4.4 Liver enzyme and bilirubin elevations

Liver enzyme and bilirubin elevations will be reported using the three following definitions:

- (ALT and/or AST ≥ 3 fold ULN) AND bilirubin ≥ 2 fold ULN^[1]
 - And ALKP ≥ 2 xULN
 - And ALKP < 2 xULN
- ALT ≥ 5 fold ULN and/or AST ≥ 5 fold ULN
- ALT ≥ 3 fold ULN and/or AST ≥ 3 fold ULN

^[1] These elevations are defined within a time window of 30 days i.e. the elevation of bilirubin should appear within 30 days after the elevation of AST and/or ALT.

The proportion of patients presenting signs of hepatic injury will be summarised, based on the following definition for signs of hepatic injury:

- ALT and/or AST ≥ 8 fold ULN
- ALT and/or AST ≥ 3 fold ULN and total bilirubin ≥ 2 fold ULN in the same sample
- ALT and/or AST ≥ 3 fold ULN and unexplained INR > 1.5 in the same sample
- ALT and/or AST ≥ 3 fold ULN and unexplained eosinophilia ($>5\%$) in the same sample
- ALT and/or AST ≥ 3 fold ULN and appearance of fatigue, nausea, vomiting, right upper abdominal quadrant pain or tenderness, fever and/or rash within ± 7 days of the abnormal ALT and/or AST laboratory test result (please refer to [Section 9.6](#) for the list of relevant MedDRA preferred terms to support the derivation of a potential hepatic injury)

In addition, maximum individual elevations based on worst value on treatment will be defined as:

- ≥ 3 fold ULN; ≥ 5 fold ULN; ≥ 8 fold ULN for AST and ALT
- ≥ 1.5 fold ULN; ≥ 2 fold ULN for bilirubin
- ≥ 1.5 fold ULN; ≥ 2 fold ULN for ALKP
- ≥ 1 fold ULN; ≥ 3 fold ULN for GGT

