6.7 BASELINE, TIME WINDOWS AND CALCULATED VISITS

As a general rule, the last assessment/measurement before the date of first trial drug intake (included) will be used as baseline (possibly last screening assessment if no further available value).

Endpoints which are censored at Week 52 will be cut on Day 373 which is calculated as: Date of first trial drug intake (i.e. Day 1) + 372 (=365+7 day window per the CTP flow chart). All references to Day 373 throughout this document refer to this date which is 372 days after the date of first trial drug intake.

Visit windowing will be performed as described in [Tables 6.7: 1](#), [6.7: 2](#) and [6.7: 3](#), in order to assign data to the relevant study visit based on the actual day of the assessment. Data will be analysed using the re-calculated visits in the statistical tables. However, in the listings, all

visits performed will be displayed (even if outside time-window), along with the re-calculated visit.

Table 6.7: 1 Time windowing rules for spirometry, physical exam, vital signs, HCRU, mRSS, Digital ulcer, menstruation calendar

Time window of actual day ^[1]			Allocated to		
Start day	End day (included)	Length of the time-window [days]	Visit number	Visit name	Planned day of the visit
Last assessment before the date of first trial drug intake	1	1	1 or 2 ^[2]	Baseline	1
2	22	21	3	2 weeks	15
23	36	14	4	4 weeks	29
37	64	28	5	6 weeks	43
65	127	63	6	12 weeks	85

Table 6.7: 1 Time windowing rules for spirometry, physical exam, vital signs, HCRU, mRSS, Digital ulcer, menstruation calendar (cont'd)

Time window of actual day ^[1]			Allocated to		
128	211	84	7	24 weeks	169
212	309	98	8	36 weeks	253
310	373	63	9	52 weeks	365
374	533	161	10	68 weeks	477
534	645	112	11	84 weeks	589
646	708	63	12	100 weeks	701
709	Last trial drug intake + 27 ^[3]	Variable	NA	Between 100 weeks and follow-up visit	NA
Last trial drug intake + 28	Last trial drug intake + 35 ^[3]	7	FU	Follow-up	NA

Note: mRSS and Digital ulcer not measured at visits 3, 4, 5 and follow-up

[1] First trial drug intake date is taken into account as a reference to calculate time windows

[2] Depending on the last assessment before first trial drug intake (included), refer to [Section 6.7](#) for baseline definition

[3] These two periods only exist if follow-up visit occurs after 709 days (included)

Table 6.7: 2 Time windowing rules for SGRQ, FACIT-dyspnoea, SHAQ, EQ-5D-5L, patient global VAS, DLCO, SpO2, antoantibody assessment, Physician global VAS

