If after windowing of visits at baseline, two values fall within the same baseline interval, then the last value will be taken into account. If after windowing of post-baseline visits, two visits fall in the same interval, then the measurement closest to the planned visit will be taken into account. In case two measurements are equidistant from the planned visit, then the last one will be picked.

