7.8 SAFETY ANALYSIS

All safety analyses will be performed on the TS.

Safety analysis will primarily be based on data collected within the first 52 weeks. Additional safety analysis will also be presented for safety data collected overall including data collected beyond 52 weeks. See [Section 6.1](#) of this document for further details of the treatment period specifications and refer to [Table 6.1: 1](#) for the start and end dates for these analyses.

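### The SAP does not settle which laboratory samples the 52-week liver elevation table counts: the visit-window rule in 6.7 conflicts with the worst-value and 30-day rules in 5.4.4

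*SAP*

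**What the plan says.** **SAP 7.8.2 (Laboratory data)** plans two liver outputs. For the first, "In addition a thorough description of liver enzymes and bilirubin elevations over the whole study period will be given", following the definitions in SAP 5.4.4, with maximum individual elevations and a Kaplan-Meier plot. No visit windows are mentioned. For the second, "A similar summary table of liver enzymes and bilirubin elevations over the first 52 weeks will also be provided", with a cross-reference to Table 6.7: 3 for the time windows.

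**SAP 6.7 (Baseline, time windows and calculated visits)** gives the general rule: "Data will be analysed using the re-calculated visits in the statistical tables". Only listings show every visit performed. If, after windowing post-baseline data, "two visits fall in the same interval, then the measurement closest to the planned visit will be taken into account". No exception is written for elevation or worst-value tables.

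**SAP 5.4.4 (Liver enzyme and bilirubin elevations)** defines ALT/AST counts at 3 and 5 times ULN, a combined ALT/AST and bilirubin elevation in which bilirubin may follow by up to 30 days, and signs of hepatic injury. It then adds that "maximum individual elevations based on worst value on treatment will be defined as" a set of ULN multiples.

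**SAP Table 6.1: 1** sets the 52-week on-treatment laboratory period by dates: from first intake to last intake plus 28 days, or to Day 373 if intake continued to that day or beyond.

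**SAP 7.8** states: "Safety analysis will primarily be based on data collected within the first 52 weeks".

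**The concern.** The protocol itself generates liver samples between scheduled visits. After an elevation that calls for close observation, Protocol 4.2.1.2 asks for re-tests within 48 to 72 hours, "then approximately 7 days, then approximately 2 weeks by using intermediate visit lab kit". It also asks for weekly or two-weekly monitoring after some restarts. Section 4.2.2.2 adds two-weekly liver tests for about six weeks when certain co-medications are introduced, section 5.3.7.1 calls for an unscheduled test when hepatic symptoms appear without results, and section 6.2.4 adds laboratory samples at dose-change visits.

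Several samples of one liver episode can therefore fall in one window. If the nearest-day rule governs the 52-week table, the retained sample will usually be the scheduled one, and a higher later value will not count. Two programmers working correctly from this SAP could then produce different 52-week counts for an adverse event of special interest. Because the pointer is attached to the 52-week table only, that table and the whole-trial table could also disagree for the same patient.

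**Working it through.** The plan states no figure to reproduce. The check sets the rules side by side and then applies the literal one.

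**1. Window lengths.** Inputs are the start and end days in Table 6.7: 3; length = end − start + 1.

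| Visit | Days | Length | Planned day |
|---|---|---|---|
| 6 | 65–106 | 42 | 85 |
| 6a | 107–148 | 42 | 127 |
| 7 | 149–190 | 42 | 169 |
| 7a | 191–232 | 42 | 211 |
| 8 | 233–281 | 49 | 253 |
| 8a | 282–337 | 56 | 309 |
| 9 | 338–373 | 36 | 365 |

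The windows run from 36 to 56 days. The Visit 9 length is printed as 56, but its days give 373 − 338 + 1 = 36. A two-week re-test sequence fits easily inside one such window.

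**2. Literal nearest-day rule.** Assume one sample on each of the ten planned days up to week 52 (15, 29, 43, 85, 127, 169, 211, 253, 309, 365), each followed by re-tests at +3, +7 and +14 days. That gives 10 × 3 = 30 re-tests.

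- 27 share a window with a sample nearer the planned day and are dropped.
- 1 falls after Day 373 (365 + 14 = 379).
- 2 are kept: 15 + 14 = 29 and 29 + 14 = 43. Both are themselves planned visit days, so no separate re-test survives.

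If the three intervals are read as consecutive (+3, +10, +24 days), 28 are dropped, 2 fall after Day 373 and none is kept. These are counts of samples under assumed timings, not of patients. The triggering scheduled sample is always kept, so information is lost only where a later value is higher.

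**3. One invented patient.** ALT is 3.5 × ULN on Day 169, 9 × on Day 172 and 6 × on Day 176. All three fall in the Visit 7 window, at distances 0, 3 and 7 days from Day 169.

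- SAP 6.7 read literally keeps 3.5 ×. The patient counts at 3 × ULN, but not at 5 × or under the 8 × hepatic-injury criterion.
- The worst-value rule in SAP 5.4.4 puts the same patient at 9 × in the maximum-elevation display.

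Both instructions can be read as applying to the same 52-week output.

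**4. The 30-day rule.** Gaps between successive planned laboratory days, from Visit 3 to Visit 9, are 14, 14, 42, 42, 42, 42, 42, 56 and 56 days. From Visit 5 onward every gap exceeds 30. On planned days, two separate retained samples could therefore never meet the rule. Where both visits may move by 7 days, the shortest possible gap is 42 − 14 = 28 days, so it could be met only at the edges. Pairs within one sample are unaffected. SAP 5.4.4 thus appears to assume that all samples are available.

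**5. Reach of the worst-value wording.** It introduces only the last block of SAP 5.4.4. The counts at 3 × and 5 × ULN, the combined elevation and the hepatic-injury signs carry no such wording.

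**The case against.** A reader might infer that liver peaks will drop out of the trial's main liver safety summary and that a treatment difference will be understated. The documents do not support that.

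- The 52-week table is to resemble the whole-study description, which follows SAP 5.4.4 and its worst-value rule. A specific rule may reasonably be taken to override a general one.
- The 30-day pairing makes little sense with one sample per window, so the authors probably intended all samples.
- The pointer has an innocent reading. SAP 5.4.6 cites Table 6.7: 1 merely to mark a period boundary, and Table 6.7: 3 has a break at Day 373. It may mean no more than the 52-week cut.
- If the general sentence in SAP 6.7 governs all statistical tables, both liver tables are windowed; if the worst-value rule governs, neither is. The tables disagree only if the pointer is what brings the windows into play.
- The fuller liver description covers the whole study. Time to onset and the patient graphs carry no windowing pointer, listings show all visits, and hepatic-injury events of special interest are reported by investigators.
- SAP 7.8.2 relies on a sponsor standard for laboratory data that is not available here and may settle the matter.

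Most of this stands. It shows that loss of peaks is not certain, and that calling the 52-week table the main liver summary goes too far. It does not remove the conflict: inheriting the worst-value rule through the word similar is an inference, that rule does not reach the threshold counts, and Day 373 is already defined in the text of SAP 6.7, so the pointer is not needed for the cut.

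**Conclusion.** The point holds as an unresolved conflict between SAP rules, not as demonstrated data loss. SAP 7.8.2 and 6.7, read literally, use one sample per window for the 52-week liver table. SAP 5.4.4 and Table 6.1: 1 imply every on-treatment sample within a date range.

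The direction under the literal reading is clear: using a subset of samples can only lower, or leave unchanged, the number of patients with an elevation, a combined elevation or signs of hepatic injury. The size is not known. The 27-of-30 illustration depends on that reading and on assumed sampling days. The documents do not say how often a re-test exceeds the scheduled value and crosses a threshold, nor how that would differ between arms. It is still worth correcting, because the first 52 weeks are the primary safety period and the remedy is small.

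**What to change.** In SAP 7.8.2, replace the reference to Table 6.7: 3 with the on-treatment period of Table 6.1: 1, cut at Day 373. Write the cut out, because for a last intake between Day 346 and Day 372 the rule of last intake plus 28 days runs past Day 373 (346 + 28 = 374).

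Add that all liver elevation, hepatic-injury and maximum-elevation analyses, over 52 weeks and over the whole trial, use every on-treatment central laboratory sample, including unscheduled and re-test samples. State that the nearest-to-planned-day rule applies to by-visit summaries only.

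This costs about two sentences and no new data. Reported elevation counts may be slightly higher than under the windowed reading.

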7.8.3 Vital signs

Summary statistics will be presented for observed values and change from baseline by treatment and visit. This will be performed for the overall timeframe.

The frequency of patients with marked changes in vital signs over 52 weeks will also be summarised by treatment according to the definitions in [Section 5.4.5](#) of this document.

7.8.4 ECG

Not applicable as ECG findings will be reported as adverse events.

7.8.5 Others

Clinically relevant findings after Doppler echocardiography will be reported as adverse events.

Any worsening of trial indication SSc-ILD will be reported and summarised as AEs.

In addition, information collected at Week 52 about relevant changes in echocardiography characteristics (based on Echocardiography eCRF page) will be summarised using descriptive statistics.

9. ADDITIONAL SECTIONS

9.1 HCRU (HEALTH CARE RESOURCE UTILISATION)

Descriptive statistics of HCRU over time will be provided in Section 16.1.13.1 of the CTR. Nevertheless, the economic modelling of the HCRU data will not be part of the clinical trial report but reported separately.

9.2 COMPLEMENTARY INFORMATION ON STATISTICAL MODEL AND SAS CODE

Primary endpoint model (and other rate of decline endpoints):

The key code is given below. Time is defined as duration since first trial drug intake divided by 365.25. Visit is the visit number.

Meanbase corresponds to the overall mean baseline for the endpoint.

```
proc MIXED data=FVC cl method=reml order= formatted covtest;
  CLASS patient visit treatment gender ata;
  MODEL endpoint= gender age height ata fvcbaseline fvcbaseline*time
  treatment treatment*time /solution CL ddfm=KR;
  RANDOM intercept time/ type=un subject=patient;

  ESTIMATE 'Nintedanib' fvcbaseline*time MEANBASE treatment*time 0 1 /
e CL;
  ESTIMATE 'Placebo' fvcbaseline*time MEANBASE treatment*time 1 0 / e
CL;
  ESTIMATE 'Nintedanib 150mg bid - Placebo' treatment*time -1 1 / e CL;
RUN;
```

Primary endpoint subgroup analysis model:

This is the case of subgroups with 2 categories:

```
proc MIXED data=FVC cl method=reml order= formatted covtest;
  CLASS patient visit treatment gender ata subgroup;
  MODEL endpoint= gender age height ata fvcbaseline fvcbaseline*time
  treatment*subgroup treatment*subgroup*time /solution CL ddfm=KR;
  RANDOM intercept time/ type=un subject=patient;

  ESTIMATE 'Nintedanib - Subgroup A' fvcbaseline*time MEANBASE treatment *
subgroup *time 0 0 1 0 / cl e;
  ESTIMATE 'Placebo - Subgroup A' fvcbaseline*time MEANBASE treatment *
subgroup *time 1 0 0 0 / cl e;

  ESTIMATE 'Nintedanib - Subgroup B' fvcbaseline*time MEANBASE treatment *
subgroup *time 0 0 0 1 / cl e;
  ESTIMATE 'Placebo - Subgroup B' fvcbaseline*time MEANBASE treatment *
subgroup *time 0 1 0 0 / cl e;

  ESTIMATE 'Nintedanib - Placebo Subgroup A' subgroup * treatment *time -1
0 1 0 / e CL;
```

```
'Week 52, Subgroup 3'  
0 0 0 0 0 0 0 0  
0 0 0 0 0 0 0 0  
0 0 0 0 0 0 0 0  
0 0 0 0 0 0 0 0  
0 0 0 0 0 0 0 0  
0 0 0 0 0 0 0 0  
0 0 0 0 0 0 0 0  
1 1 -3 1 -1 -1 3 -1,
```

```
'Week 52, Subgroup 4'  
0 0 0 0 0 0 0 0  
0 0 0 0 0 0 0 0  
0 0 0 0 0 0 0 0  
0 0 0 0 0 0 0 0  
0 0 0 0 0 0 0 0  
0 0 0 0 0 0 0 0  
0 0 0 0 0 0 0 0  
1 1 1 -3 -1 -1 -1 3
```

```
/divisor=4 joint elsm cl alpha=0.05;  
RUN;
```

For 2 subgroups, the LSMESTIMATE will write:

```
LSMESTIMATE visit*treatment*subgroup
```

```
'Week 52, Subgroup 1'  
0 0 0 0  
0 0 0 0  
0 0 0 0  
0 0 0 0  
0 0 0 0  
0 0 0 0  
-1 1 1 -1,
```

```
'Week 52, Subgroup 2'  
0 0 0 0  
0 0 0 0  
0 0 0 0  
0 0 0 0  
0 0 0 0  
0 0 0 0  
1 -1 -1 1
```

```
/divisor=2 joint elsm cl alpha=0.05;
```

Implementation of multiple imputation:

The following steps provide a guidance of how missing FVC data at week 52 will be implemented in patients of pattern 3 and 4 using multiple imputation. Refer to [Table 7.4.2.1.2: 1](#) for the description of patterns and the different sensitivity analyses regarding handling of missing data.

1. Run the MMRM of the primary analysis (either including patients of pattern 2 only for sensitivity analyses 1 and 2 or on all patients for sensitivity analysis 3) to get the slope estimates (SE) by treatment group. Let $\hat{\beta}_D$ and $\hat{\sigma}_D$ denote the slope (SE) estimates in Nintedanib 150 mg and $\hat{\beta}_P$ and $\hat{\sigma}_P$ the slope (SE) estimates in placebo.
2. Let β_D and β_P represent the true slopes in drug and placebo respectively with $f(\beta_D) \sim N(\hat{\beta}_D, \hat{\sigma}_D^2)$ and with $f(\beta_P) \sim N(\hat{\beta}_P, \hat{\sigma}_P^2)$, using the slope (SE) estimates obtained in step 1.
3. Imputation of missing week 52 data in patients of pattern 3:

Multiple impute missing values (1000 imputations per patient). To do so, draw random slopes from the distributions defined in step 2. Considering that the withdrawal of a patient leading to missing data can occur at any time during the study, the timepoint of the last available FVC value has to be taken into account to impute the missing FVC value at 52 weeks.

$$\text{FVC week 52 imputed}_{ij} = \text{last FVC value available}_i + \hat{\beta}_{ij}(\text{time between date of last FVC value available}_i \text{ and planned 52 week timepoint [days]})$$

where i denotes the indicator of the i^{th} patient, j the indicator of the j^{th} imputation and $\hat{\beta}_{ij}$ denotes a random slope sampled from the distribution mentioned in step 3a for the i^{th} patient in the j^{th} imputation. Depending on the sensitivity analysis, use either random slopes drawn from $f(\beta_D)$ for patients randomised to Nintedanib 150 mg in sensitivity analysis 1 or $f(\beta_P)$ for all patients in sensitivity analyses 2 and 3.

4. Imputation of missing week 52 data in patients of pattern 4:

Multiple impute missing values (1000 imputations per patient). To do so, draw random slopes from the truncated distribution $f(\beta_P)/2$ restricted to the interval $(-\infty, \hat{\beta}_P]$ defined in step 2.

See step 3 for further details on how to use these slopes to impute the missing values at week 52.

5. Run the MMRM of the primary analysis on each imputed dataset, using a "by _IMPUTATION_" statement.
6. Combine the estimates obtained in step 5 using PROC MIANALYZE.

